2.0 OBJECTIVES AND SCIENTIFIC AIMS

Primary objective:

To evaluate the 2-month progression-free survival (PFS) of sorafenib in patients with metastatic or recurrent esophageal and gastroesophageal (GE) junction cancer.

Secondary objectives:

a) To evaluate the overall response rate (partial response and complete response) of sorafenib.

b) To evaluate the tolerability and adverse event profile of sorafenib in this patient population.

c) To perform an exploratory analysis of differential response between squamous cell carcinoma and adenocarcinoma.

d) To evaluate phosphorylated extracellular signal-regulated kinase (pERK) expression in tumor tissue and correlate with tumor response.

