- Sorafenib diary to be collected.
- A CBC, CMP and amylase/lipase level. For patients on coumadin, a PT/INR/PTT level.

Immunohistochemistry for pERK

Phosphorylated extracellular signal-regulated kinase (pERK) determination through immunohistochemical (IHC) staining of prior paraffin stored tumor blocks or unstained slides. pERK determination may be pending at the time of protocol registration, with prior material submitted for IHC during the course of protocol therapy. The pERK status is not required for enrollment on the protocol. Studies will be performed at MSKCC.

Whenever possible, the most recent tumor biopsy/pathologic specimen prior to study enrollment will be used.

Paraffin-embedded tissue should be prepared by fixing tissues in 10% neutral buffered formalin. An optimal fixation time is 12 - 24 hours and should not exceed 48 hours. Slides should consist of a minimum of five unstained, positively charged microscope slides with $4 - 6 \mu m$ tissue sections, cut from a paraffin block. The slides should be prepared in a 37 - 42 °C water bath without gelatin. Only one $4 - 6 \mu m$ cut section is placed on each slide, opposite the frosted end, before the slides are allowed to air dry.

pERK tissue expression is assayed using a rabbit polyclonal antibody for pERK (phosphop44/42 mitogen activated protein kinase [Thr202/Tyr204]; Cell Signaling Technology Inc, Danvers, MA). A standard secondary biotinylated anti-mouse antibody and streptavidin horseradish peroxidase are then applied for visualization.

Briefly, the procedure involves: (1) Deparaffinization and rehydration of the tissues with xylene and graded alcohols; (2) Antigen unmasking by pretreatment with sodium citrate; (3) Incubation with primary antibody or negative control sera (non-specific mouse IgG); (4) Incubation with secondary biotinylated anti-mouse antibody; (5) Incubation with streptavidin horseradish peroxidase; (6) Incubation with substrate and chromogen (DAB) (7) Counterstaining the tissue with hematoxylin-eosin; (8) Mounting with an aqueous cover slip medium and; (9) Microscopy.

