A positive control cell line (derived from a gastrointestinal stromal tumor cell line that expresses pERK) is included with each assay. Each specimen is reviewed after staining for the presence of tumor cells, the localization of pERK staining to the cell nuclei or the cytoplasm, the staining intensity and the proportion of tumor cells that stain positive. pERK staining is graded semi-quantitatively using a five-point scale: 0, no staining; 1+, weak; 2+, moderate; 3+ strong and; 4+, intense.

Amended: 05/12/15

IRB#: 09-016A(9)

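### Section 10 pairs a rabbit pERK primary antibody with an anti-mouse secondary and a mouse IgG negative control; the species must be reconciled before secondary objective d has a valid measurement.

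*Combined protocol and SAP*

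**What the plan says.** The pERK assay is described once, in the immunohistochemistry part of Section 10. On the primary antibody it says: "pERK tissue expression is assayed using a rabbit polyclonal antibody for pERK". On detection it says: "A standard secondary biotinylated anti-mouse antibody and streptavidin horseradish peroxidase are then applied for visualization". The numbered procedure that follows repeats the detection reagent in step (4), "Incubation with secondary biotinylated anti-mouse antibody", and gives the control in step (3) as "Incubation with primary antibody or negative control sera (non-specific mouse IgG". No anti-rabbit reagent and no rabbit IgG control appears anywhere in the protocol.

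Two further statements bear on the point. On the positive control: "A positive control cell line (derived from a gastrointestinal stromal tumor cell line that expresses pERK) is included with each assay". On scoring: "pERK staining is graded semi-quantitatively using a five-point scale", running from 0 to 4+. Section 10 does not say what happens to a run whose controls fail.

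The result feeds secondary objective d in Section 2: "To evaluate phosphorylated extracellular signal-regulated kinase (pERK) expression in tumor tissue and correlate with tumor response". Section 14 plans Fisher's exact test for it and treats any finding as hypothesis-generating.

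**The concern.** In indirect immunohistochemistry the secondary antibody has to recognise immunoglobulin from the species in which the primary was raised. The negative control has to be immunoglobulin of that same species, so that any non-specific binding by the primary would also show in the control. Section 10 meets neither condition. Its secondary matches the negative control and not the primary, so the only immunoglobulin that the detection step is built to recognise is the one meant to be the blank.

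At stake is whether a reported pERK score means anything. This is the only measurement described for objective d, and Section 6.1 makes tissue for this stain an inclusion criterion. A reader cannot reproduce the assay from the protocol, or tell from it whether staining was specific.

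**Working it through.** The plan states no figure for this point, so the check is mainly a comparison of text.

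**Species at each mention in Section 10**

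| Component | Where | Species named |
|---|---|---|
| Primary antibody | Assay description | Rabbit |
| Secondary antibody | Assay description | Directed against mouse |
| Negative control | Step (3) | Mouse IgG |
| Secondary antibody | Step (4) | Directed against mouse |

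One mention says rabbit and three say mouse. The wording is complete and the secondary is repeated, so this is not a gap left by text extraction.

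**What the controls would show under each possible set of reagents**

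| Primary / secondary / negative control | Positive control line | Negative control |
|---|---|---|
| Rabbit / anti-mouse / mouse IgG (as written) | Should fail to stain specifically | Is the reagent that the secondary recognises |
| Rabbit / anti-rabbit / mouse IgG (only the secondary corrected) | Stains | Looks clean whether or not rabbit IgG binds non-specifically |
| Rabbit / anti-rabbit / rabbit IgG | Stains | Informative |
| Mouse / anti-mouse / mouse IgG | Stains | Informative |

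The first row should be caught by the positive control. The second row would not be: both controls would look as they should, while false positive staining went unseen. On a graded scale that starts at weak staining, non-specific binding could move a specimen from 0 to 1+ or higher. Only the last two rows give a valid measurement.

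**Consequence for the planned test, worst case only.** Suppose no specimen stained and all 35 scored 0. The pERK-positive row of the 2×2 table is then empty. With that margin at zero and k responders, only one table is possible. Its probability is C(k,0) × C(35−k,0) / C(35,0) = 1, so p = 1.0 for any k and the odds ratio is undefined. Runs with k = 2, 4 and 6 gave this result. It shows that the analysis would be empty in that case; it does not predict that the case will occur.

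**Reach.** The primary rule in Section 14 (22 or more of 35 alive and progression free at 2 months) does not use pERK. Its exact binomial properties are P(X ≥ 22 | 35, 0.50) = 0.088 and P(X ≥ 22 | 35, 0.72) = 0.915, within the stated 10% error rates. Response rate and toxicity do not use pERK either.

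**The case against.** The strongest reply is that the text shows an inconsistency and not a failed assay. Three of the four mentions agree on mouse. If rabbit is the misplaced word, the reagents form a coherent set and nothing fails. The procedure is introduced as a brief summary, and the staining is done in-house. Section 3.5.4 reports that the same group scored pERK by immunohistochemistry in an earlier sorafenib trial and found a correlation with time to progression (p=0.0003). The protocol does not say that the reagents were the same, but this makes a drafting slip the likelier explanation. All of this stands, and it is why the point asks for reconciliation and does not presume which word is wrong.

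The positive control is a second reply, and it stands in part. It should expose a secondary that does not detect the primary, and staining of archived tissue is not tied to enrolment, so a failed run need not be final. It does not expose an unmatched negative control, and no rule ties scoring to the controls.

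Third, the analysis carries little weight. At the response rates in Section 14, 35 patients give about 0.05 × 35 = 1.75 to 0.18 × 35 = 6.3 responders, so Fisher's test would be weak even with a sound assay. That bears on priority; it does not remove the contradiction.

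A reader might go further and infer that essentially no tumour would stain, where the 36% positivity in the gefitinib trial cited in Section 3.4 implies 0.36 × 35 = 12.6, or about 13 of 35. The documents do not support this. The 36% comes from another trial, and its assay details and cut-off are not given here. This protocol sets no positivity cut-off, and zero staining would require every run to proceed despite a failed positive control. An anti-mouse reagent might also cross-react with rabbit IgG and give some signal, though an uncontrolled one. A loss of scarce tissue to failed runs is likewise not shown: five slides is a minimum, and blocks may be used.

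**Conclusion.** The species mismatch is real, is stated twice for the secondary antibody, and is corrected nowhere else. Followed literally, Section 10 cannot validly measure pERK. That conclusion rests on the general requirement that the secondary and the negative control match the primary's species, and on reading Section 10 as it is printed. It is not a finding that the laboratory ran the wrong assay; the documents cannot show which reagents were used.

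The size is small: one exploratory secondary analysis. This is a minor correction, but a needed one. An informal change to the secondary alone would satisfy the positive control and leave the negative control uninformative.

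**What to change.** In Section 10, reconcile the primary antibody, both mentions of the secondary, and the negative control against the laboratory's validated procedure:

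- If the primary is rabbit, name a biotinylated anti-rabbit secondary in both places and non-immune rabbit IgG as the negative control.
- If a mouse primary is used, correct the description of the primary and leave the rest.

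Then add one sentence: a run is scored only if its positive control stains and its species-matched negative control does not.

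The cost is a few changed words, one added sentence and a check with the laboratory. Sample size, the primary decision rule and the planned Fisher's test stay as they are.

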11.0 TOXICITIES/SIDE EFFECTS

11.1 General considerations

Subjects must be carefully monitored for adverse events. This monitoring includes clinical laboratory tests. Adverse events should be assessed on a continuous basis, with the highest grade recorded according to National Cancer Institute Common Terminology Criteria for Adverse Events (NCI-CTCAE), version 3.0.⁴⁶ Adverse event should be assessed in terms of seriousness, severity, and relationship to the study drug (See Section 11.6).

11.2 General toxicity profile

For the most recent safety update, refer to the Nexavar® Prescribing Information. The overall safety profile of sorafenib is based on 1,286 cancer patients, who received sorafenib as a single agent.³³

Table 11.2.1 will be used to determine the "expectedness" of adverse drug reactions used for reporting of adverse events to Regulatory Agencies. It is not a complete list of adverse events reported in clinical trials.

System Organ Class	Very Common	Common	Uncommon
	≥ 10%	≥1% to <10%	$\geq 0.1\%$ to < 1%
Infections and infestations			Folliculitis infection
Blood and lymphatic system	Lymphopenia	Leukopenia	
disorders		Neutropenia	
		Anemia	
		Thromboc ytopenia	
Immune system disorders			Hypersensitivity reactions
			(including skin reactions and
			urticaria)
Endocrine disorders			Hypothyroidism
Metabolism and nutrition	Hypophosphatemia	Anorexia	Hyponatremia
disorders			Dehydration
Psychiatric disorders		Depression	
Nervous system disorders		Peripheral sensory	Reversible posterior
		neuropathy	leukoencephalopathy*
Ear and labyrinth disorders		Tinnitus	
Cardiac disorders			Myocardial ischemia and
			infarction*
			Congestive heart failure*
Vascular disorders	Hemorrhage (including		Hypertensive crisis*
	gastrointestinal* and		
	respiratory tract* and		
	cerebral hemorrhage*)		
	Hypertension		

Table 11.2.1. Adverse drug reactions in patients in multiple clinical trials.

IRB#:09-016A(9)

* Events may have a life-threatening or fatal outcome. Such events are uncommon. **Palmar plantar erythrodysaethesia reaction

IRB PB

IRB#: 09-016A(9)

System Organ Class	Very Common ≥10%	Common ≥1% to <10%	Uncommon ≥ 0.1% to < 1%
Respiratory, thoracic and mediastinal disorders		Hoarseness	Rhinorrhea
Gastrointestinal disorders	Diarrhea Nausea Vomiting	Constipation Stomatitis (including dry mouth and glossodynea) Dyspepsia Dysphagia	Gastroesophageal reflux disease Pancreatitis Gastritis Gastrointestinal perforation*
Hepato-biliary disorders			Increase in bilirubin and jaundice
Skin and subcutaneous tissue disorders	Rash Alopecia Hand-foot reaction** Pruritis Erythema	Dry skin Dermatitis exfoliative Acne Skin desquamation	Eczema Erythema multiforme minor
Musculoskeletal, connective tissue and bone disorders		Arthralgia Myalgia	
Reproductive system and breast disorders		Erectile dysfunction	Gynecomastia
General disorders and administration site conditions	Fatigue Pain (inc. mouth, abdominal, bone pain, headache and tumor pain)	Asthenia Fever Influenza-like illness	
Investigations	Increased amylase Increased lipase	Weight decreased Transient increase in transaminases	Transient increase in blood alkaline phosphatase INR abnormal, prothrombin level abnormal

* Events may have a life-threatening or fatal outcome. Such events are uncommon. **Palmar plantar erythrodysaethesia reaction

11.3 Laboratory abnormalities

The following laboratory abnormalities were observed in the randomized phase III trial of sorafenib in patients with advanced renal cell carcinoma³³:

Elevated lipase and amylase: Elevated lipase and amylase levels were very commonly reported. Grade 3/4 lipase elevations occurred in 12% of patients in the sorafenib group compared to 7% of patients in the placebo group. Grade 3/4 amylase elevations were reported

IRB#:09-016A(9)

in 1% of patients in the sorafenib group compared to 3% of patients in the placebo group. Clinical pancreatitis was reported in 2 of 451 sorafenib treated patients (Grade 4) and 1 of 451 patients (Grade 2) in the placebo group.

Hypophosphatemia: Hypophosphatemia was a common laboratory finding, observed in 45% of sorafenib treated patients compared to 12% of placebo patients. Grade 3 hypophosphatemia (1-2 mg/dl) occurred in 13% of sorafenib-treated patients and 3% of patients in the placebo group. There were no cases of Grade 4 hypophosphatemia (< 1 mg/dl) reported in either sorafenib or placebo patients. The etiology of hypophosphatemia associated with sorafenib is not known.

Lymphopenia: Grade 3/4 lymphopenia was reported in 13% of sorafenib treated patients and 7% of placebo patients.

Neutropenia: Grade 3/4 neutropenia was reported in 5% of sorafenib treated patients and 2% of placebo patients.

Anemia: Anemia was observed in 44% of sorafenib-treated patients and 49% of placebo patients. Grade 3/4 anemia was reported in 2% of sorafenib-treated patients and 4% of placebo patients.

Thrombocytopenia: Thrombocytopenia was observed in 12% of sorafenib-treated patients and 5% of placebo patients. Grade 3/4 thrombocytopenia was reported in 1% of sorafenib-treated patients and 0% of placebo patients.

11.4 Special warning and precautions for use

Dermatological toxicities: Hand-foot skin reaction (palmar-plantar erythrodysaesthesia) and rash represent the most common adverse drug reactions with sorafenib. Rash and hand-foot skin reaction are usually Grade 1/2 and generally appear during the first six weeks of treatment with sorafenib. Management of dermatologic toxicities may include topical therapies for symptomatic relief, temporary treatment interruption and/or dose modification of sorafenib, or in severe or persistent cases, permanent discontinuation of sorafenib. See Section 9.2.4 for supportive measures and Table 11.5.1 for suggested dose modifications for hand-foot reaction.

Hypertension: An increased incidence of hypertension was observed in sorafenib-treated patients. Hypertension was usually mild to moderate, occurred early in the course of treatment and was amenable to management with standard antihypertensive therapy. Blood pressure should be monitored regularly and treated, if required, in accordance with standard medical practice. In cases of severe or persistent hypertension, or hypertensive crisis despite adequate antihypertensive therapy, permanent discontinuation of sorafenib should be considered. See Table 11.5.2 for suggested dose modifications for treatment-emergent hypertension.

IRB#: 09-016A(9)

Hemorrhage: An increase in the risk of bleeding may occur following sorafenib administration. The incidence of severe bleeding events is uncommon. If any bleeding event necessitates medical intervention, it is recommended that permanent discontinuation of sorafenib be considered.

Wound healing complications: No formal studies of the effect of sorafenib on wound healing have been conducted. In patients undergoing major surgical procedures, temporary interruption of sorafenib therapy is recommended for precautionary reasons. There is limited clinical experience regarding the timing of reinitiation of therapy following major surgical intervention. Therefore, the decision to resume sorafenib therapy following a major surgical intervention should be based on clinical judgment of adequate wound healing.

[figure not shown]
Cardiac Ischemia and/or Infarction: In the phase 3 randomized study of sorafenib in patients with advanced renal cell carcinoma, the incidence of treatment-emergent cardiac ischemia/infarction events was higher in the sorafenib group (2.9%) compared with the placebo group (0.4%).⁴¹ Patients with unstable coronary artery disease or recent myocardial infarction were excluded from this study. Sorafenib should be discontinued in patients who develop cardiac ischemia and/or infarction.

Gastrointestinal perforation: Gastrointestinal perforation is an uncommon event and has been reported in <1% of patients taking sorafenib.³³ In some cases, this was not associated with apparent intra-abdominal tumor. Sorafenib should be discontinued in patients with GI perforation.

Effects on ability to drive and use machines: No studies on the effects of sorafenib on the ability to drive or use machines have been performed. There is no evidence that sorafenib affects the ability to drive or operate machinery.

Patients with Hepatic Impairment: *In vitro* and *in vivo* data indicate that sorafenib is primarily metabolized by the liver. Systemic exposure and safety data were comparable in patients with Child-Pugh A and B hepatic impairment. Sorafenib has not been studied in patients with Child-Pugh C hepatic impairment. No dose adjustment is necessary when administering sorafenib to patients with Child-Pugh A and B hepatic impairment.

Patients with Renal Impairment: Sorafenib has not been studied in patients with severe renal impairment (CrCl <30 mL/min) or in patients undergoing dialysis. **Carcinogenesis, Mutagenesis, Impairment of Fertility:** Carcinogenicity studies have not been performed with sorafenib. Sorafenib was clastogenic when tested in an *in vitro* mammalian cell assay (Chinese Hamster Ovary) in the presence of metabolic activation. Sorafenib was not mutagenic in the *in vitro* Ames bacterial cell assay or clastogenic in an *in vitro* present in the final drug substance (<0.15%), was positive for mutagenesis in an *in vitro* bacterial cell assay (Ames test) when tested independently. No specific studies with sorafenib

IRB#:09-016A(9)

have been conducted in animals to evaluate the effect on fertility. However, results from the repeat-dose toxicity studies suggest there is a potential for sorafenib to impair reproductive performance and fertility. Multiple adverse effects were observed in male and female reproductive organs, with the rat being more susceptible than mice or dogs. Typical changes in rats consisted of testicular atrophy or degeneration, degeneration of epididymis, prostate, and seminal vesicles, central necrosis of the corpora lutea and arrested follicular development. Sorafenib-related effects on the reproductive organs of rats were manifested at daily oral doses =30 mg/m² (approximately 0.5 times the AUC in cancer patients at the recommended human dose). Dogs showed tubular degeneration in the testes at 600 mg/m²/day (approximately 0.3 times the AUC at the recommended human dose) and oligospermia at 1200 mg/m²/day of sorafenib. Adequate contraception should be used during therapy and for at least 2 weeks after completing therapy. ³³

Pediatric Use: The safety and effectiveness of sorafenib in pediatric patients have not been studied. Repeat dosing of sorafenib to young and growing dogs resulted in irregular thickening of the femoral growth plate at daily sorafenib doses = 600 mg/m^2 (approximately 0.3 times the AUC at the recommended human dose), hypocellularity of the bone marrow adjoining the growth plate at 200 mg/m²/day (approximately 0.1 times the AUC at the recommended human dose), and alterations of the dentin composition at 600 mg/m²/day. Similar effects were not observed in adult dogs when dosed for 4 weeks or less.

Geriatric Use: In total, 32% of RCC patients treated with sorafeniab were age 65 years or older, and 4% were 75 and older. No differences in safety or efficacy were observed between older and younger patients, and other reported clinical experience has not identified differences in responses between the elderly and younger patients, but greater sensitivity of some older individuals cannot be ruled out.

Drug-Drug Interactions: Caution is recommended when administering sorafenib together with compounds that are metabolized/ eliminated predominantly by the UGT1A1 pathway (e.g. irinotecan) ³³

CYP3A4 inducers: There is no clinical information on the effect of CYP3A4 inducers on the pharmacokinetics of sorafenib. Inducers of CYP3A4 activity (e.g. rifampicin, Hypericum perforatum also known as St. John's wort, phenytoin, carbamazepine, phenobarbital, and dexamethasone) may increase metabolism of sorafenib and thus decrease sorafenib plasma concentrations.

CYP3A4 inhibitors: Ketoconazole, a potent inhibitor of CYP3A4, administered once daily for 7 days to healthy male volunteers did not alter the mean AUC of a single 50 mg dose of sorafenib. Therefore, clinical pharmacokinetic interactions of sorafenib with CYP3A4 inhibitors are unlikely.

IRB#: 09-016A(9)

CYP2C9 substrates: The possible effect of sorafenib on the metabolism of the CYP2C9 substrate warfarin was assessed indirectly by measuring PTINR. The mean changes from baseline in PT-INR were not higher in sorafenib patients compared to placebo patients, suggesting that sorafenib did not inhibit warfarin metabolism *in vivo*. However, patients taking warfarin should have their INR checked regularly.

CYP isoform-selective substrates: Concomitant administration of midazolam, dextromethorphan and omeprazole, which are substrates of cytochromes CYP3A4, CYP2D6 and CYP2C19, respectively, following 4 weeks of sorafenib administration did not significantly alter the exposure of these agents. This indicates that sorafenib is neither an inhibitor nor a clinically meaningful inducer of these cytochrome P450 isoenzymes.

Combination with other anti-neoplastic agents: In clinical studies, sorafenib has been administered together with a variety of other antineoplastic agents at their commonly used dosing regimens, including gemcitabine, oxaliplatin, doxorubicin, and irinotecan. Sorafenib had no effect on the pharmacokinetics of gemcitabine or oxaliplatin. Concomitant treatment with sorafenib resulted in a 21% increase in the AUC of doxorubicin. When administered with irinotecan, whose active metabolite SN-38 is further metabolized by the UGT1A1 pathway, there was a 67-120% increase in the AUC of SN-38 and a 26-42% increase in the AUC of irinotecan. The clinical significance of these findings is unknown. However, caution is recommended when administering sorafenib with doxorubicin and with compounds that are metabolized/eliminated predominantly by the UGT1A1 pathway (e.g. irinotecan).

Warfarin: Infrequent bleeding events or elevations in the International Normalized Ratio (INR) have been reported in some patients taking warfarin while on sorafenib therapy. Patients taking warfarin concomitantly should be monitored regularly for changes in prothrombin time, INR and for clinical bleeding episodes.

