11.5 Dose delay/modification

Intrapatient dose reduction will be allowed depending on the type and severity of toxicity encountered provided that criteria for patient withdrawal from study treatment have not been met. The dose levels for sorafenib are as described below:

Starting dose 0	Sorafenib 400 mg twice daily
Dose level -1	Sorafenib 400 mg daily
Dose level -2	Sorafenib 400 mg every other day

If further dose reduction is required, the patient should be taken off-protocol.

Patients who require a treatment delay of >4 consecutive weeks should also be taken offprotocol.

IRB#:09-016A(9)

The following tables describe the recommended dose modifications for sorafenib-associated toxicities, including hand-foot skin reaction (Table 11.5.1), treatment-emergent hypertension (Table 11.5.2), exacerbation of baseline hypertension (Table 11.5.3) and other general hematologic and non-hematologic toxicities (Table 11.5.4).

Grade	Occurrence	Suggested Dose Modification		
Grade 1 Numbness, dysesthesia, paresthesia, tingling, painless swelling, erythema or discomfort of the hands or feet which does not disrupt the patient's normal activities	Any	Promptly institute supportive measures such as topical therapy for symptomatic relief and continues orafenib treatment.		
Grade 2 Painful erythema and swelling of the hands or feet and/or discomfort affecting the patient's	First	 Promptly institute supportive measures such as topical therapy for symptomatic relief and consider a decrease of sorafenib dose to 400 mg daily for a minimum of 7 days and up to 28 days. If toxicity resolves to grade 0-1 after dose reduction, increase sorafenib back to full dose of 400 mg BID. 		
normalactivities		• If toxicity does not resolve to grade 0-1 despite dose reduction, interrupt sorafenib treatment for a minimum of 7 days and until toxicity has resolved to grade 0-1.		
		• When resuming treatment after dose interruption, resume sorafenib at a reduced dose of 400mg daily.		
		• If toxicity is maintained at grade 0-1 at reduced dose for a minimum of 7 days and up to 28 days, increase sorafenib back to full dose of 400 mg BID		
	Second or Third occurrence	As for first occurrence. Upon resuming sorafenib treatment, decrease dose by one dose level (400 mg daily or 400 mg every other day).		
		Decision whether to dose re-escalates hould be based on clinical judgment and patient preference.		

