CTCAE v3.0 definitions Grade 1: asymptomatic, transient (<24 hrs) increase by > 20 mmHg (diastolic) or > 150/100 if previously				
WNL; intervention not indicated Grade 2: recurrent or persistent (>24 hrs) or symptomatic increase by >20 mmHg (diastolic) or to >150/100 if previously WNL; monotherapy may be indicated. Grade 3: requiring more than one drug or more intensive therapy than previously Grade 4: life threatening (a g hypertensive arisis)				

Grade 4: life threatening (*e.g.*, hypertensive crisis)

Table 11.5.3: Suggested dose modifications for sorafenib for exacerbation of hypertension in patients with baseline diagnosis of hypertension.

Amended: 05/12/15

IRB#:09-016A(9)

Hypertension grade	Suggested dose modification		
Grade 1: Asymptomatic, transient (<24 hours)	Increase blood pressure monitoring		
increase by >20 mmHg (diastolic) or to			
>150/100 mmHg if previously within normal			
limits (WNL)			
Grade 2: Recurrent or persistent (\geq 24 hours)	Additional anti-hypertensive therapy per		
increase by >20 mmHg (diastolic) or to	standard management and continue sorafenib		
>150/100 mmHg if previously WNL			
OR			
Grade 3: Requiring >1 drug or more intensive			
therapy than previously			
BUT diastolic blood pressure <110 mmHg			
Grade 2 but symptomatic	1. Hold sorafenib until symptoms resolve and		
OR	diastolic BP <100 mmHg		
Diastolic blood pressure ≥110 mmHg	2. Additional anti-hypertensive therapy.		
	3. Restart sorafenib at one dose level lower.*		
	4. If diastolic BP is ≥ 100 mmHg on anti-		
	hypertensive therapy, decrease by another		
	dose level.		
Grade 4: Life-threatening consequences, e.g.	Discontinue sorafenib; institute supportive		
hypertensive crisis	measures		

*may be able to resume sorafenib at full-dose later if BP is <140/80 on anti-hypertensive therapy.

Table 11.5.4: Dose modifications for sorafenib hematologic and non-hematologic toxicities			
(other than hand-foot reaction and hypertension)			

Toxicity	Grade 1	Grade 2	Grade 3*	Grade 4*
Non-	Continue at the	Continue at the	Withhold dose for at	Withhold dose for

Amended: 05/12/15

IRB PB

IRB#: 09-016A(9)

hamatalagia	same dose level.	same dose level.	loget 7 davis until	at logat 7 days until
hematologic	same dose level.	same dose level.	least 7 days until	at least 7 days until
			toxicity is grade ≤ 1 ,	toxicity is grade
			then resume	≤ 1 , then resume
			treatment at one dose	treatment at one
			level lower.	dose level lower,
				or discontinue at
				the discretion of

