				the principal
				investigator after
				discussion with
				study sponsor.
Hematologic	Continue at the	Continue at the	Withhold dose for at	Withhold dose for
	same dose level.	same dose level.	least 7 days until	at last 7 days until
			toxicity is grade <2,	toxicity is grade
			then resume	≤ 2 , then resume
			treatment at one dose	treatment at one
			level lower.	dose level lower,
				or discontinue at
				the discretion of
				the principal
				investigator after
				discussion with
				study sponsor.

*Patients who develop grade 3 fever/chills, grade 3 elevation of hepatic transaminases with ALT and AST <10X ULN, grade 3 hyperlipasemia or hyperamy lasemia without clinical or other evidence of pancreatitis, grade 3 leukopenia, or grade 3/grade 4 lymphopenia may continue study treatment without interruption at the discretion of the investigator.

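### Section 11.4 says to discontinue sorafenib after cardiac ischemia/infarction or GI perforation, but Table 11.5.4 does not exempt these events and directs a lower-dose restart at grade 3; precedence is not explicit

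*Combined protocol and SAP*

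**What the plan says.** Section 11.4 gives event-specific warnings. On the heart: "Sorafenib should be discontinued in patients who develop cardiac ischemia and/or infarction". On the gut: "Sorafenib should be discontinued in patients with GI perforation". Neither sentence has a grade threshold or a restart route.

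Section 11.5 sets out the dose-modification tables. Table 11.5.4 is titled "Dose modifications for sorafenib hematologic and non-hematologic toxicities", with one exclusion in brackets: "other than hand-foot reaction and hypertension". Its non-hematologic row gives:

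- Grades 1-2: stay on the same dose.
- Grade 3: withhold for at least 7 days until grade 1 or lower, then resume "treatment at one dose" level lower. The cell has no discontinuation option.
- Grade 4: the same, "or discontinue at" the principal investigator's discretion after talking to the sponsor.

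A footnote lists further exceptions (for example, certain grade 3 laboratory findings) for patients who "may continue study treatment without interruption at the discretion of the investigator". Neither cardiac ischemia/infarction nor GI perforation is on that list.

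Section 9.1 sends the reader to Section 11.5 for dose changes and to Section 13 for stopping criteria. Section 13 names neither event; it lists unacceptable adverse events as determined in Section 11.

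**The concern.** Both events are non-hematologic and neither is excluded from Table 11.5.4, so each falls under two instructions. An investigator who stops treatment after a grade 3 event follows Section 11.4. One who withholds and restarts at a lower dose follows the table. Neither could clearly be called a protocol deviation.

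Table 11.2.1 marks both events as ones that may be life-threatening or fatal, so the first stake is safety. The second is consistent handling: tolerability is a secondary objective, and the count of patients who stop for toxicity depends on which passage was followed.

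**Working it through.** **Side-by-side reading.**

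| Grade of event | Section 11.4 | Table 11.5.4, non-hematologic row | Can both be followed? |
|---|---|---|---|
| 1-2 | Discontinue | Continue, same dose | No |
| 3 | Discontinue | Withhold, then resume one level lower | No, if the patient recovers in time to resume |
| 4 | Discontinue | Withhold and resume lower, or discontinue | Yes, by stopping |

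At grade 3 the clash is limited further: resuming needs recovery to grade 1 or lower, and a delay of more than 4 consecutive weeks takes the patient off protocol under Sections 11.5 and 13.

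**Does anything settle precedence?** Three places bear on it.

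1. Section 11.5 allows dose reduction only while the criteria for withdrawal from treatment are not met. This puts withdrawal ahead of the tables.
2. The withdrawal criteria are in Section 13, which for adverse events refers back to Section 11. That section contains both Section 11.4 and Table 11.5.4, so the reference does not choose between them.
3. Section 11.4 does link to the tables where it covers hand-foot reaction (Table 11.5.1) and hypertension (Table 11.5.2), and Table 11.5.4 excludes exactly those two. No such link exists for the two events at issue.

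Section 11.4 also words its warnings differently: for bleeding that needs intervention and for severe hypertension, discontinuation is to be considered; for these two events it is stated outright. That shows the wording in 11.4 is firm, but not that it overrides the table.

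**How often could it arise?** The plan gives no figure of its own. With n = 35 (Section 14), the chance of at least one event is 1 - (1 - p)^35.

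- Ischemia/infarction, p = 0.029 (Section 11.4, renal cancer trial): 1 - 0.971^35 = 0.643, about 64%.
- Perforation, p below 0.01 (Section 11.4): at the ceiling, 1 - 0.99^35 = 0.297, so under 30%.
- Ischemia/infarction with shorter exposure. Assumption: risk is proportional to time on drug, taking median PFS of 5.5 months in the renal trial (Section 3.5.3) against about 2 months here (Section 3.2, inactive therapy). Then p = 0.029 × 2/5.5 = 0.0105, and 1 - 0.9895^35 = 0.31, about 31%.
- Table 11.2.1 places myocardial ischemia and infarction in the 0.1% to under 1% class. At the top of that class the chance is again under 30%.

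These rates are not split by grade. The documents give no grade distribution, so the chance of an event in the grades where the passages strictly clash cannot be computed; it can only be lower than the any-grade figure at the same rate.

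**The case against.** The strongest reply is that the protocol already ranks the passages. Section 11.5 makes dose reduction conditional on withdrawal criteria not being met. Section 13 makes unacceptable adverse events such a criterion and looks to Section 11 to define them. Section 11.4 is where discontinuation is stated for these two events, whereas the grade 3 cell of the table declares nothing unacceptable. Section 9.1 likewise separates dose changes from stopping, and the text of Section 11.5 presents Table 11.5.4 as covering the remaining general toxicities and as recommendations. Specific text over a general table is a natural reading.

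Much of this stands: many investigators would reach Section 11.4 by this route. But it is an inference in several steps. Section 13 points to the whole of Section 11, neither passage refers to the other, and a table that lists exceptions in both its title and its footnote gives no sign that further exceptions lie elsewhere.

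The reply is also right that stopping at grade 4 complies with both passages, and that the analysis is little affected. Under Section 12.6, patients taken off for toxicity while alive with stable or responding disease are not censored and are counted. The rule in Section 14 (22 or more of 35 alive and progression-free at 2 months) does not use the reason for stopping, and toxicities are simply tabulated.

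**Conclusion.** The inconsistency is real and rests on the text alone. It is strict at grade 3 and at grades 1-2. At grade 4 it is weaker: Section 11.4 states discontinuation, the table only permits it. Cross-references suggest an order of precedence but do not state one. The consequence is for patient safety and uniform handling; no primary-endpoint calculation or decision rule depends on it.

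A reader might infer three stronger things that the documents do not support:

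- **That the conflict is likely to arise in this trial.** The 64% and the under-30% figures are any-grade chances at rates from other settings, and the ischemia figure falls to about 31% under the exposure assumption above. None isolates the clashing grades.
- **That perforation is nearly certain to occur.** Applying the 6% in Section 3.2 would give 1 - 0.94^35 = 0.885, about 89%. That rate is for perforation or near-perforation on bevacizumab with cisplatin and irinotecan, a different drug given in combination, and should not be used here.
- **That a grade 4 event meets two opposite orders.** The grade 4 cell allows discontinuation, so stopping satisfies both.

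Whether esophageal or GE junction disease itself changes the risk on sorafenib is not addressed by the documents' rates; they are illustrative only, and the point does not depend on them.

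**What to change.** Reconcile Section 11.4 with Table 11.5.4:

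1. Add a cross-reference, either in the table's title or footnote (naming the events governed by Section 11.4) or in Section 11.4 (pointing to the table).
2. State which passage takes precedence for cardiac ischemia/infarction and GI perforation, and whether this holds at every grade.
3. Put the same link in Section 13, so that its reference to Section 11 leads to one rule.

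Which clinical rule applies is for the sponsor and the investigators to decide. The cost is about one line in each place; sample size, endpoint and analysis do not change.
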